### **10.2 Dietary Restrictions**

Alcohol may increase symptoms of drowsiness or sudden onset of sleep that can be caused by pramipexole. Subject will be requested to limit alcoholic consumption to one glass of wine or one shot a day, and not within three hours before or after taking the study medication.

Dietary tyramine restriction is not ordinarily required with recommended doses of rasagiline. However, certain foods (e.g. aged cheeses, such as stilton cheese) may contain very high amounts (i.e. 150 mg) of tyramine and could potentially cause a hypertensive "cheese" reaction in subjects taking rasagiline, even at recommended doses, due to mild increased sensitivity to tyramine.

### **10.3 Rescue Therapy**

No rescue therapy will be allowed during the treatment phase and the two weeks afterwards up until the safety follow up visit. If needed by the subject for adequate treatment of subject's Parkinson's symptoms and according to the Investigator's judgment the study medication will be discontinued and a rescue medication may be administered. This will be recorded on the concomitant medications log and in the reasons for treatment termination. Subject, who stopped taking study treatment prior to Visit 6, should return to the site for an Early Treatment Termination (ETT) visit as soon as possible. ETT subjects will be requested to continue with study visits and activities as planned, for follow up, without taking any study medication.

## **11 LABORATORIES**

### **11.1 Safety Laboratory Tests**

The safety laboratory tests (chemistry, hematology, coagulation and urinalysis see Appendix II), conducted at screening, safety follow up visit, and additional liver function or kidney function tests, as needed, will be carried out by the Eurofins Central Laboratory EU, [name] for sites in Europe and Eurofins Central Laboratory US [name] for sites in USA and Canada.

The tests will be done according to Eurofins Central Laboratory written Standard Operating Procedures. Any value outside the normal range will be flagged for the attention of the Investigator or designee at the site. The Investigator or designee will indicate whether or not the value is of clinical significance.

Any clinically important abnormal laboratory values noted at the Screening visit will be recorded as medical history. In addition, in order for the Sponsor to collect additional information about clinically important laboratory abnormalities, at minimum, the following laboratory abnormalities should be captured from Baseline and onwards on the AE pages of the eCRF as appropriate:

- Any laboratory test result that meets the criteria for an AE or SAE;
- Any laboratory abnormality that requires the subject to have study drug discontinued or interrupted;
- Any laboratory abnormality that requires the subject to receive specific corrective therapy.

All clinically important abnormal laboratory tests occurring during the study will be repeated in appropriate intervals until: (1) the value returns to Baseline, (2) the value is judged to be clinically acceptable by the Investigator and the Sponsor, (3) a diagnosis that explains the abnormal laboratory is made or (4) subject is lost to follow-up. When possible, the Investigator should report the clinical rather than the laboratory term (e.g., anemia versus low hemoglobin.)

The central laboratory will perform all clinical laboratory tests. Detailed shipping/handling instructions of laboratory supply will be provided in a separate laboratory manual.

## **11.2 Vital Signs, Height and Weight**

Respiration rate (RR per minute) and temperature will be measured, with the subject in the seated position for at least 5 minutes, at the visits specified in the Schedule of Activities.

Orthostatic measurements (lying and standing BP and 30 seconds of radial pulse) can be measured manually or using an automated BP machine and will be measured at every clinic visit, except visit 3 that is done for titration evaluation of Pramipexole ER or matching placebo. The subject's BP and HR will be measured after the subject has been lying for approximately 5 minutes. The subject will be instructed to rise to a standing position, and a BP measurement will be taken after the subject has been standing for 3 minutes. HR will be determined for a period of 30 seconds.

All BP and HR measurements will be taken using the writing arm of each subject.

Additional vital signs will be obtained at the discretion of the Investigator if clinically significant signs or symptoms occur.

The subject's weight will be measured at every clinic visit except visit 3 that is done for titration evaluation of Pramipexole ER or matching placebo. The subject's height will only be measured at the Screening visit.

### **11.3 Electrocardiograms (ECG)**

A standard 12-lead ECG will be performed at Screening, Baseline and Week 14/ETT. Additional ECGs will be performed if clinically indicated. ECGs will be conducted after approximately 5 minutes supine or recumbent rest using a standard ECG machine equipped with computer-based interval measurements.

The Investigator is responsible for evaluating the ECG interpretation in relationship to clinical signs and symptoms and reaching a medical decision regarding the subject's medical status. The ECG findings should be assessed by the Investigator as normal, abnormal not clinically significant (NCS), or abnormal clinically significant (CS), as appropriate. All abnormalities, whether assessed as clinically significant or not, will be recorded. The ECG tracing should be initialed and dated by the Investigator.

## **12 STUDY DRUGS SUPPLY**

### **12.1 Drug Manufacturing**

Capsules of P2B001, its individual components (pramipexole and rasagiline) and matching placebo were manufactured by Catalent Pharma solutions Somerset, USA, address: [name].

Pramipexole ER tablets and matching placebo were purchased from [name] Limited, [name]

All bottle closures are tamper proof and child resistant.

### **12.2 Treatment Assignment and Randomization**

All subjects will be assigned a unique subject number at the screening visit (visit 1). The subjects found to be eligible for the study by both PI and the EMC will be randomized as soon as possible in order to trigger shipment of investigational medication to the subject. At randomization, the subject will be given a unique randomization number which will be entered into the database but not used for subject follow-up. The same unique subject number allocated in the screening visit will continue to be the subject ID number for the rest of the study.

The randomization will be managed by a cloud-based Randomization and Trial Supply Management (RTSM) system of Medidata-Balance using a randomization list comprised of permuted blocks, with stratification by region. Allocation will be to the next available record in

the randomization list which corresponds to the appropriate stratum. Medication will be assigned based on the treatment group allocated at randomization.

Study files will keep track of subject number and medication kit number. In case of medication kit loss or the patient ran out of drug for any reason the site can get a replacement medication kit by contacting the RTSM in order to get the appropriate medication kit number.

### **12.3 Packaging and Labeling**

The study medication will be packed and labeled by Almac Group limited, [name].

The study kit will include an outer box containing 4 inner boxes;

- Weeks 1-4 box containing three bottles: one bottle of capsules of either P2B001/RAS 0.75/PPX 0.6/placebo once daily (33 capsules) (bottle C, labeled with a blue stripe), one bottle with tablets of either Pramipexole ER 0.375 mg or matching placebo (30 tablets), (bottle A, labeled with a yellow stripe) and one bottle with either Pramipexole ER 1.5 mg or matching placebo (30 tablets), (bottle B, labeled with a pink stripe).
- Two identical boxes for weeks 5-12. Each box containing 4 bottles: one bottle of capsules of either P2B001/RAS 0.75/PPX 0.6/Placebo (33 capsules) and 3 identical bottles with Pramipexole ER 1.5 mg or matching placebo tablets (30 tablets each).
- Week 13 One box containing two bottles: one bottle of tablets of either Pramipexole ER 0.375 mg or matching placebo (30 tablets) and one bottle of tablets of either Pramipexole ER 1.5 mg or matching placebo

For subject's convenience the bottles are labeled with different colored stripes. The bottle of P2B001/RAS 0.6/PPX 0.75/placebo is labeled with a blue stripe named bottle C. The bottle of Pramipexole ER 0.375 mg/matching placebo is labeled with a yellow stripe named bottle A and the bottle of Pramipexole ER 1.5 mg/matching placebo is labeled with a pink stripe named bottle B.

The whole study kit with the 4 inner boxes will be dispensed to the subject on visit 2. No further dispensing is needed on other visits. The subject will be requested to bring the used inner box with him/her for the next visit as follows:

- Visit 4: return of box weeks 1-4.
- Visit 5: return of box used during weeks 5-8 (1 out of 2 Week 5-12).
- Visit 6: return of box used during weeks 8-12 (2 out of 2 Week 5-12).
- Visit 7: return of box week 13

Since this product is intended for once daily dosing, there is no need for the subject to carry the medication with him/her throughout the day, therefore, the subject will be instructed to keep the

bottles with the kit box throughout the study. The outer box and each inner box will tamper evident sealed.

The master English version of the labels on the bottles will include at least the following information as follows:

Label for P2B001 /RAS 0.75mg / PPX 0.6mg / placebo bottle:

- Study number: P2B001/003
- Kit number
- Subject number
- Subject initials
- Site number
- Contents: 33 capsules, containing: Pramipexole / Rasagiline once daily 0.6/0.75 mg or Pramipexole 0.6 mg or Rasagiline 0.75 mg or placebo (Exp: mm/yyyy)
- Storage conditions: 59°F - 77°F (15°C - 25°C).
- Protect from exposure to high humidity.
- Take 1 capsule by mouth with a glass of water (8oz or 240ml), do not chew, crush or cut. For further dosing instructions see “dosing instruction leaflet” provided by the clinical staff.
- Packaging batch number
- Caution: new Drug Limited by Federal (or United States) law to Investigational use / for clinical trial use only/ Investigational drug. To be used by qualified investigators only.
- Keep out of the reach of children.
- Do not remove or ingest moisture resistant bags or canisters from the bottle.
- Return all empty, partially used or unused bottles from the current box to the clinic for accountability.
- Sponsor name and location

Label for Pramipexole ER tablets 1.5 mg / matching placebo bottle:

- Study number: P2B001/003
- Kit number
- Subject number
- Subject initials
- Site number
- Bottle # \_\_\_\_ out of \_\_\_\_\_
- Contents: 1 x 30 tablets, containing Pramipexole 1.5 mg or placebo (exp: mm/yyyy)
- Storage conditions: 59°F - 77°F (15°C - 25°C).

- Take caplet/s by mouth with a glass of water (8oz or 240ml), do not chew, crush or cut. For further dosing instructions see “dosing instruction leaflet” provided by the clinical staff.
- Packaging batch number
- Caution: new Drug Limited by Federal (or United States) law to Investigational use / for clinical trial use only/Investigational drug. To be used by qualified investigators only.
- Keep out of the reach of children.
- Do not remove or ingest moisture resistant bags or canisters from the bottle.
- Return all empty, partially used or unused packages from the current box to the clinic for accountability.
- Sponsor name and location
- Protect from exposure to high humidity.
- Please keep the bottles with the kit box together at all times.

Label for Pramipexole ER tablets 0.375 mg / matching placebo bottle:

- Study number: P2B001/003
- Kit number
- Subject number
- Subject initials
- Site number
- Contents: 1 x 30 tablets, containing Pramipexole 0.375 mg or placebo (exp: mm/yyyy)
- Storage conditions: 59°F - 77°F (15°C - 25°C).
- Take tablet/s by mouth with a glass of water (8oz or 240ml), do not chew, crush or cut. For further dosing instructions see “dosing instruction leaflet” provided by the clinical staff.
- Packaging batch number
- Caution: new Drug Limited by Federal (or United States) law to Investigational use / for clinical trial use only/Investigational drug. To be used by qualified investigators only.
- Keep out of the reach of children.
- Do not remove or ingest moisture resistant bags or canisters from the bottle.
- Return all empty, partially used or unused packages from the current box to the clinic for accountability.
- Sponsor name and location
- Protect from exposure to high humidity
- Please keep the bottles with the kit box together at all times.

The following information will be included on the Inner boxes label (up titration box, maintenance box and down titration box):

- Study number: P2B001/003
- Box type (either weeks 1-4, Weeks 5-12, Weeks 13)
- Kit number
- Subject number
- Subject initials
- Investigator name
- Site number
- Contents (one or more of the following, as relevant):
  - 33 capsules, containing: Pramipexole / Rasagiline once daily 0.6/0.75 mg or Pramipexole 0.6 mg or Rasagiline 0.75 mg or placebo. (Exp: mm/yyyy)
  - 30 tablets, containing Pramipexole 1.5 mg or placebo (Exp: mm/yyyy)
  - 30 tablets, containing Pramipexole 0.375 mg or placebo (Exp: mm/yyyy)
- Storage conditions: 59°F - 77°F (15°C - 25°C). Take by mouth with a glass of water (8oz or 240ml), do not chew, crush or cut. For further dosing instructions see “dosing instruction leaflet” provided by the clinical staff.
- Packaging batch number
- Caution: new Drug Limited by Federal (or United States) law to Investigational use / for clinical trial use only/Investigational drug. To be used by qualified investigators only.
- Keep out of the reach of children.
- Return all empty, partially used or unused packages from the current box to the clinic for accountability.
- Sponsor name and location
- Protect from exposure to high humidity
- Please keep the bottles with the kit box together at all times.

The following information will be included in the Outer box label:

- Study number: P2B001/003
- Kit number
- Earliest expiry date
- Subject number
- Subject initials
- Investigator name
- Site number

- Kit content
- Storage conditions: 59°F - 77°F (15°C - 25°C).
- Packaging batch number
- Caution: new Drug Limited by Federal (or United States) law to Investigational use / for clinical trial use only/Investigational drug. To be used by qualified investigators only.
- Keep out of the reach of children.
- Sponsor name and location
- Protect from exposure to high humidity
- Take by mouth with a glass of water (8oz or 240ml), do not chew, crush or cut.
- For further dosing instructions see "dosing instruction leaflet" provided by the clinical staff.

Specific information or language required for sites in Canada and Europe will be included according to local regulations of each country. The kit label to Canadian sites will include at least a French translation. The kit label to the European sites will include the relevant translation per the main language of the European country

#### **12.4 Distribution and Shipment**

Study drugs will be shipped to the study site, under the sponsor's responsibility.

The study drugs will be shipped and stored in room temperature between 15° and 25°C (59°F-77°F). Protect from exposure to high humidity and light.

All study drugs and materials will be packed in appropriate storage boxes.

If, upon arrival at the investigational site, the study drugs appear to be damaged, the sponsor should be contacted immediately.

Each shipment of study drugs for the study will contain a shipment form describing the content of shipment. This form will assist in maintaining current and accurate inventory records. When a shipment is received, the site Investigator/coordinator/pharmacist or depot will acknowledge receipt of the study drugs by signing the relevant shipping documents.

#### **12.5 Storage, Dispensing and Return**

The study drugs will be kept in a secure, limited-access, controlled storage area.

Only authorized personnel will have access to the study drugs. The study site personnel at each site will be responsible for correct storage and handling of the study drugs. Drug storage temperature will be monitored and recorded on a daily basis.

The study drugs will be dispensed by the study site pharmacist or by other authorized personnel. All unused capsules/tablets and all full, empty or partially empty bottles will be returned to the sponsor by the site monitor after a full reconciliation of the site's study drug inventory against the site's drug accountability records has been performed.

The retest dates will be managed by the Randomization Trial Supply Management (RTSM) system.

### **12.6 Verification of Compliance with Treatment Regimen**

Subjects will be instructed to bring the last medication box used (open and unopened bottles) with them to visits 4, 5, 6 and 7 for compliance and accountability checks. During each study visits, (visits 4-7), the Investigator and/or site coordinator will assess the subject's compliance with the prescribed regimen for the study medication. This will include checks of protocol compliance and use of study drug in order to assess the reliability of subject-generated data. Subjects who fail to comply with the study requirements may be withdrawn from the study, following consultation with the sponsor.

Compliance with the dosing regimen will be determined by performing study drug accountability of returned study drugs used and unused. The number of used, unused and lost capsules will be recorded in the study drug accountability records and the eCRF by site personnel at every post randomization visit.

A subject will be considered non-compliant if he/she misses more than 4 doses of study medication within a 28 day period (less than 85% compliance). Examples of reasons for missing a dose are 1) if a subject develops an adverse event that the Investigator believes requires the subject's dose to be held, or 2) if a subject loses their kit of study medication and a replacement kit is requested, which should arrive at the site within 1-2 days (3-4 days if a weekend is involved).

### **12.7 Accountability**

For study drug accountability, the subject will be requested to bring for visits 4-7, all empty, partially used or unused bottles from the box used during the previous month. During these visits (visits 4, 5, 6/ETT and 7) the site staff will count the remaining capsules and tablets that the subject brought with him and document the results in accountability records. Only the opened box that was used during the last visit will be brought for the accountability. Accountability of the entire study medications kit (with all boxes and bottles left) will be done at ETT visit for ETT subjects.

The Investigator is responsible for the control of study drugs under investigation. Adequate records of the receipt and disposition of the study drug must be maintained.

Study drugs accountability records should contain the following information:

- Shipment number, kit numbers, batch number, number of kits and date received for all shipments of study drug received by the site
- Subject number, medication kit number, the date, batch number, and quantity of study drug dispensed to AND returned by the subject (when applicable)

- Kits numbers, batch number, number of kits (un-dispensed study drug) or number of capsules/tablets (returned study drug) for all study drug returned to the Sponsor

During each site visit, the monitor will review all study drugs accountability records and study drug inventory on-site.

## **12.8 Study End**

Once the study site has been closed out by the monitor all remaining unused and partially used drug supplies must be returned to the sponsor. Once this has been done, the corresponding accountability records must be kept at the study sites and a photocopy of these records will be sent to the sponsor.

## **12.9 Blinding**

Blinding will be maintained during the whole course of the study. The Investigators, study coordinators, and their staff at the study site, the sponsor's personnel and the personnel involved in subject assessment, monitoring, analysis and data management will all be blinded to the subject assignment. Specific, independent, unblinded study personnel from the CRO will be available to provide the DSMB with periodic reports.

### **12.9.1 Emergency Code Breaking**

Emergency code breaking will be managed by the IWR/IVR system. The randomization code may be broken by the Investigator when urgent action is required for the clinical management of the patient. Typically, code breaks will occur only in emergency situations which may include the management of a serious adverse event. If possible, the sponsor, or designee, should be contacted to discuss the case before the code is broken.

If it becomes necessary to break the code during the study, the name of the person who breaks the code, the date, time and reason will be recorded in the RTSM. The reason for the break of the code should also be documented in the eCRF. The Investigator should promptly document and explain to the Sponsor, or designee, any premature unblinding (e.g., accidental unblinding, unblinding due to a serious adverse event) of the investigational product.

## **13 SAFETY/ADVERSE EVENTS**

### **13.1 Adverse Events definition**

An adverse event is any untoward medical occurrence in a clinical investigation subject who is administered a medicinal product whether or not considered related to the medicinal product. An AE can therefore be any unfavorable and unintended sign (including an abnormal laboratory finding, for example), symptom or disease (new or exacerbated), temporally associated with the

use of a medicinal product, whether or not considered related to the product. Pre-existing signs and symptoms should not be considered AEs unless they worsen unexpectedly post-study drug administration. In addition, any study procedure-related AE that occurs after study participants have signed the Informed Consent Form (ICF) and prior to administration of the first dose of study drug will be recorded as an AE. Any adverse event that occurs post-study drug administration will be considered a treatment-emergent AE. Any adverse event that occurs prior-study drug administration will be considered a baseline-emergent AE. Again, all events should be entered whether or not the event is considered to be related to the study drug.

The date of onset, a description of the AE, severity, seriousness, action taken, relationship to the study drugs (causality), outcome of the event and date of resolution will be recorded. The final study report will include all of these details for each AE as well as the calculated duration.

The Investigator will assess the severity of the AE as:

- mild: AE which is easily tolerated
- moderate: AE sufficiently discomforting to interfere with daily activity.
- severe: AE which prevents normal daily activities.

The Investigator will assess the causality of the AE as (see section 13.2):

- unrelated
- possibly related
- probably related

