### 13.2 AE Causality Definitions

TERM	DEFINITION	CLARIFICATION
Unrelated	This category applies to those AEs which, after careful consideration, are clearly due to extraneous causes (disease, environment, etc.)	
Possibly	This category applies to those AEs for which, after careful medical consideration at the time they are evaluated, a connection with the test drug administration appears unlikely but cannot be ruled out with certainty.	An AE may be considered possibly related if or when (at least two of the following): 
 
• It follows a reasonable temporal sequence from administration of the drug.
 
• A causal relationship to the experimental treatment cannot be reasonably excluded and an alternative explanation (e.g., concomitant medication or concomitant disease) cannot be excluded or reasonably suggested as causing the AE.
 
• It follows a known pattern of response to the test drug.
 

Probably	This category applies to those AEs which, after careful medical consideration at the time	An AE may be considered probably related if or when (at least three of the following):

TERM	DEFINITION	CLARIFICATION
	they are evaluated, are felt with a high degree of certainty to be related to the test drug.	
 
• It follows a reasonable temporal sequence from administration of the drug.
 
• It could not be reasonably explained by the known characteristics of the subject's clinical state, environmental or toxic factors or other modes of therapy administered to the subject.
 
• It disappears or decreases on cessation or reduction in dose. There are important exceptions when an adverse event does not disappear upon discontinuation of the drug, yet drug-relatedness clearly exists.
 
• It follows a known pattern of response to the test drug.
 

In case of an AE, the Investigator will initiate appropriate treatment according to his medical judgment and will decide whether to withdraw the subject from the study. Subjects should be followed clinically until all parameters (including laboratory tests) have either returned to normal, or are otherwise explained.

An abnormal result of diagnostic procedures including abnormal laboratory findings will be considered an AE if it:

- results in subject's withdrawal by the Investigator
- is associated with a serious adverse event
- is associated with clinical signs or symptoms

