### **13.7 Suspected Unexpected Serious Adverse Reaction (SUSAR)**

Adverse reactions are all untoward and unintended responses to the investigational product related to any dose administered. Unexpected adverse reaction is those of which the nature, or severity, is not consistent with the applicable product information.

All SUSARs should be reported to the authorities.

Investigators will also be notified of all unexpected, serious, drug-related events (i.e., 7- or 15-day expedited safety reports) that occur during the clinical trial; those events will be reported to the site in a blinded fashion. Each site is responsible for notifying its IRB of these expedited safety reports, in accordance with applicable site practices.

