**15.6.11 The exploratory endpoints to be analyzed are:**

- To evaluate the efficacy of P2B001 0.6/0.75 mg compared to its individual components in the following endpoints:
  - Change from baseline to Week 12/Treatment Termination visit in each of the 8 PDQ39 subscales scores.
  - Change from baseline to Week 12/Treatment Termination visit in Health-Related Quality of Life (HRQOL) SF-12v2 questionnaire.

- Clinical Global Impression of Improvement (CGI-I) at Week 12/Treatment Termination visit.
- To evaluate the superiority of P2B001 0.6/0.75 mg over Pramipexole ER with respect to the following outcome measures:
  - Proportion (%) of patients with ESS score >10 at Week 12/Treatment Termination.
  - Proportion (%) of patients with ESS Score  $\leq$ 10 at baseline and ESS score >10 at Week 12/Treatment Termination.
  - 3-Months rate of total number of adverse events.
  - Change from baseline to Week 12/Treatment Termination in the differences in systolic and diastolic blood pressure measured during supine and standing positions.
  - Proportion (%) of patients with both symptomatic/non-symptomatic Orthostatic Hypotension.
  - 3-Months rate of total number of both symptomatic/non-symptomatic Orthostatic Hypotension.
  - Proportion (%) of patients with symptomatic Orthostatic Hypotension.
  - 3-Months rate of total number of symptomatic Orthostatic Hypotension.
  - Proportion (%) of patients with daytime sleepiness/drowsiness related AE's.
  - Proportion (%) of patients with gastrointestinal (GI) adverse events
  - Proportion (%) of patients presenting neurological adverse events
  - Change from baseline to Week 12/Treatment Termination visit in the Orthostatic Hypotension Symptoms Assessment (OHSA) question 1.
- To descriptively evaluate the comparability of P2B001 0.6/0.75 mg with reference to the calibration arm (Pramipexole ER) in total UPDRS score (defined as sum of parts II and III, scores (0-160)).

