### 15.7.1 Adverse Events

Adverse events will be recorded from the time a subject has signed the Informed Consent Form until the end of subject's study participation, including up to Week 14 Follow-Up visit, regardless of study IP administration.

The MedDRA dictionary will be used to standardize the terms used by the Investigator to describe the Adverse Events (AEs).

The following will be incorporated into the analysis of adverse events:

- As analysis of AEs can incorporate only coded AEs, it is mandatory that at the time of database lock all AEs will be coded.
- Adverse events analyses will include only the Treatment Emergent Adverse Events (TEAEs), namely, those events which started at the time of first study IP administration or afterwards. AEs lacking start day or AEs recorded on day of first study IP lacking start time will be considered as TEAE.

The following analyses are pre-planned for adverse events:

- The incidence (no. of patients) and frequency (no. of events) of most frequent TEAEs (>5% of subjects in at least one study arm) by Preferred Term (PT).
- The incidence (no. of patients) and frequency (no. of events) of TEAEs broken down by System Organ Class (SOC) and PT.
- The incidence (no. of patients) and frequency (no. of events) of TEAEs by SOC and PT in Subjects Early Discontinued from Study/Treatment.
- The incidence (no. of patients) and frequency (no. of events) of serious TEAEs by SOC and PT
- The incidence (no. of patients) and frequency (no. of events) of TEAEs when broken down by severity.
- The incidence (no. of patients) and frequency (no. of events) of TEAEs broken down by relationship to study IP.
- The incidence (no. of patients) and frequency (no. of events) of TEAEs when broken down by action taken with study IP.
- The incidence (no. of patients) and frequency (no. of events) of TEAEs when broken down by event outcome.
- Adverse Events dictionary used to code Investigator's verbatim terms will be provided.
- Individual subject listings of all SAEs, treatment emergent SAEs, TEAEs and non-TEAEs.

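### Section 13.1 contradicts itself on worsening of pre-existing symptoms, and the treatment-emergent definition in 15.7.1 turns on onset alone, so drug-related worsening may be missed

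*Protocol*

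**What the plan says.** Protocol section 13.1 opens broadly. An AE can be any unfavourable sign, "symptom or disease (new or exacerbated), temporally associated with" use of the product, related or not. Two sentences later it narrows this: "Pre-existing signs and symptoms should not be considered AEs unless they worsen unexpectedly post-study drug administration". The section ends by instructing that "all events should be entered whether or not the event is considered to be related to the study drug". It also labels AEs after dosing as treatment-emergent and those before dosing as baseline-emergent.

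Section 13.1 does not say what 'unexpectedly' means. The only definition of the term in the protocol is in section 13.7, on expedited reporting: "Unexpected adverse reaction is those of which the nature, or severity, is not consistent with the applicable product information".

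Section 15.7.1 restricts AE analyses to treatment-emergent events (TEAEs), meaning "those events which started at the time of first study IP administration or afterwards". It does not mention an increase in severity.

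The comparisons with pramipexole ER in section 15.6.11 include the total AE rate, gastrointestinal AEs, neurological AEs and "Proportion (%) of patients with daytime sleepiness/drowsiness related AE's".

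**The concern.** Section 3.1 names nausea, vomiting, constipation, orthostatic hypotension and excessive daytime sleepiness as known dopamine agonist or pramipexole effects, and says they are more pronounced at higher doses. If a site takes 'unexpectedly' in the 13.7 sense, worsening of a baseline symptom that matches one of these effects is expected and need not be entered.

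Such subjects can be enrolled. No exclusion criterion in section 7.4 names baseline sleepiness or constipation. The exploratory endpoint restricted to subjects with ESS of 10 or less at baseline supposes that others may start above 10.

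Three things are at stake: the absolute AE rates in every arm, the exploratory AE comparisons with pramipexole ER, and consistency across about 70 sites that must each interpret one undefined word. An event never entered cannot be recovered by a later analysis definition.

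**Working it through.** **Recording rule, section 13.1**

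- For recording: an exacerbated symptom is an AE, and all events are entered regardless of relatedness. In section 13.2, one criterion for a possible or probable relation is "It follows a known pattern of response to the test drug", which supposes that known reactions are recorded.
- Against recording: the sentence on pre-existing symptoms requires unexpected worsening. The instruction to enter events regardless of relatedness does not cancel this, because relatedness and expectedness are different things.
- Result: the text supports both readings. Only symptoms already present at baseline are affected.

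**Analysis rule, section 15.7.1**

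- Section 9.2.3 allows 28 days between screening and baseline, or up to 90 with sponsor approval, so an event can start after consent and before first dose.
- Section 13.1 lists onset and resolution dates among the items recorded, but no date of a change in severity. An event that keeps its pre-dose onset date and worsens on drug fails the 15.7.1 test. If the worsening is entered as a new event with its own onset, it passes.
- The sentence in 13.1 calling post-dose AEs treatment-emergent can be read as covering the worsening. The outcome therefore depends on how the site enters the event.

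**The planned figure for a pramipexole ER comparison**

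Inputs from section 15.1: 150 v 75 subjects, ESS difference 1.5, SD 3.0, two-sided 5%.

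- Standard error = 3.0 × √(1/150 + 1/75) = 0.424.
- Noncentrality = 1.5 / 0.424 = 3.54, with 223 degrees of freedom.
- Power = 94.07%, matching the stated 94.1%.

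Nothing in this depends on AE recording. The documents give no rate or power for any AE comparison.

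**How a loss would act on an AE proportion (illustration only)**

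Let *p* be the true proportion of subjects with the event and *s* the share of those subjects not recorded, by arm. Then:

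- recorded risk difference (RD) = p_ER(1 − s_ER) − p_P2B(1 − s_P2B);
- recorded risk ratio (RR) = (p_ER / p_P2B) × (1 − s_ER)/(1 − s_P2B).

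For p_P2B take the phase 2b somnolence rate in section 3.4, 8/49 = 16.3%. The value p_ER = 30% and all values of *s* are assumptions.

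| Loss P2B001 / ER | P2B001 | ER | RD (points) | RR |
|---|---|---|---|---|
| 0 / 0 | 16.3% | 30.0% | 13.7 | 1.84 |
| 10% / 10% | 14.7% | 27.0% | 12.3 | 1.84 |
| 20% / 20% | 13.1% | 24.0% | 10.9 | 1.84 |
| 30% / 30% | 11.4% | 21.0% | 9.6 | 1.84 |
| 10% / 20% | 14.7% | 24.0% | 9.3 | 1.63 |
| 20% / 10% | 13.1% | 27.0% | 13.9 | 2.07 |

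With p_ER assumed at 25% or 40% and equal loss rising from 0 to 30%, the RD falls from 8.7 to 6.1 points or from 23.7 to 16.6 points. The RR stays at 1.53 or 2.45.

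Equal proportional loss shrinks the RD by the factor (1 − s) and leaves the RR alone. The RR moves only when the loss differs by arm, and the direction follows the arm that loses more.

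**The case against.** The strongest reply is that 'unexpectedly' is loose wording, not a rule that discards data. It can mean beyond the expected course of the pre-existing condition, with no reference to the drug's known effects. The general definition and the causality criteria both point towards recording. This stands: loss is possible, not established.

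The affected comparisons are also secondary in weight. Section 15.6.10.5 places the exploratory endpoints at nominal 5% without multiplicity control, and the opening of section 15 calls pramipexole ER comparisons other than ESS descriptive. ESS is collected on a fixed schedule, and the supine-to-standing blood pressure differences are measured rather than reported as AEs. Section 13.3 has its own AE rule for orthostatic hypotension. All of this stands, although ESS does not cover nausea, constipation or neurological AEs.

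Two further points stand. SAP version 2.0, which takes precedence under section 15.13, is not among the documents reviewed and may define TEAEs differently; the addendum is silent on AEs. Section 15.7.1 also provides listings of non-TEAEs, so a pre-dose event that was entered remains visible there.

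A reader might infer that expected dopaminergic worsening does go unrecorded and that the AE comparisons with pramipexole ER are therefore diluted. The documents do not support this. Dose dependence (section 3.1) makes a larger proportional loss in the ER arm plausible, but nothing shows it, and section 12.9 keeps investigators blinded. Nor does every AE proportion shrink by a common share, because a subject with another qualifying event of the same type still counts.

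A power loss should not be inferred either. In the somnolence illustration, moving the assumed ER rate from 25% to 40% moves no-loss power from 35% to 97%, so such figures mainly reflect the assumption.

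**Conclusion.** The inconsistency in section 13.1 is real, and the onset-only wording in 15.7.1 is a separate gap. Followed literally, they allow drug-related worsening of a baseline symptom to be left out, or a pre-dose event that becomes more severe on drug to be left out of the TEAE tables.

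The size is unknown. The documents give neither the baseline prevalence of these symptoms, nor the share of events that are worsening, nor AE rates for pramipexole ER. Absolute rates may be understated in any arm. Risk differences against pramipexole ER would be understated if the proportional loss is equal or larger in that arm, provided its true rate is the higher one. The risk ratio is distorted only by unequal loss. The primary endpoint and the powered ESS comparison do not depend on either rule.

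The point is worth correcting because unrecorded events cannot be recovered and the correction is cheap. It is not evidence that the trial's safety results are misstated.

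**What to change.** - **Section 13.1:** delete 'unexpectedly'. State that a pre-existing sign or symptom is an AE if it worsens in severity or frequency after first dose, entered with the date of worsening as onset.
- **Section 15.7.1, and the SAP if it uses the same wording:** define a TEAE as an event that starts, or increases in severity, at or after first study drug administration.
- **If data collection is complete:** the addendum records blinded data review before unblinding, so new recording instructions may come too late. In that case correct the TEAE definition before unblinding, apply it to the events already entered, and report the recording limitation.

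The cost is one deletion with a clarifying sentence, one clause, and a memo to sites if recording is still open. The downside is somewhat more AE entries, including some fluctuation of Parkinson's symptoms that the UPDRS already captures.
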